#### **Analysis of results**

Baseline socio-demographic data will be compared between groups using t-tests for

continuous data and chi-square tests for categorical data. Differences in decisional conflict scores between the intervention and control groups will be compared using unpaired t-tests. Linear regression will be done to identify significant predictors of decisional conflict in this population.

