## **Abstract**

Pelvic floor disorders can significantly affect a woman's quality of life, yet many feel uncomfortable openly discussing these topics. Treatments include lifestyle modification, medications, and/or surgery. Decisional conflict arises when patients have difficulty choosing between several viable treatment options. Factors contributing to decisional conflict include biased information, poor peer support, and unaddressed fears. Effective counselling may help address these factors. Objectives of this pilot study are to assess: (1) the impact of a small-group workshop on pelvic floor disorders (urinary incontinence (UI), or pelvic organ prolapse (POP)) on decisional conflict regarding treatment options; and (2) participant satisfaction with the workshop in terms of quality of information shared, comfort with discussing pelvic health in a group setting, and perceived benefits of a nurse continence advisor and psychologist. Women  $\geq$  18 years old with urinary incontinence or pelvic organ prolapse will be randomized at the time of their first urogynecology consultation to usual care or a 90 minute workshop on either UI or POP. Five to 10 women will attend each workshop led by a nurse continence advisor and a psychologist. In both groups, decisional conflict will be measured using the validated Decisional Conflict Scale (DCS) at baseline and at the first follow-up clinic appointment. Satisfaction with the workshop will be assessed by a post-workshop survey. Demographic data will be compared between groups using t-tests for continuous data and chi-square tests for categorical data. Change in DCS score will be compared using t-tests. Linear regression analysis will be performed to identify predictors of decisional conflict. This pilot study will assess the feasibility and acceptability of an educational workshop on pelvic floor disorders and its potential impact on decisional conflict. Results of this study will inform future development of interdisciplinary, patient-centred approaches to enhanced decision making in women's health.

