An essential component of patient-centered care, *shared decision-making* promotes active participation of the patient in discussing a care plan. Shared decision-making has been defined as ‘*an approach where clinicians and patients share the best available evidence when faced with the task of making decisions, and where patients are supported to consider options, to achieve informed preferences*’. This approach may be especially applicable in clinical situations such as pelvic floor dysfunction, where quality, not quantity, of life is at stake. In these cases, effective counselling and decision-making support is essential for the development of an acceptable treatment plan.

Women presented with several viable treatment options, each with respective drawbacks and benefits, may experience decisional conflict, which can result in emotional distress, isolation, and vulnerability. Decisional conflict can be defined as “*the uncertainty about which course of action to take when choice among competing actions involved risk, loss, regret, or challenge to personal life values*”. Antenatal testing, hormone replacement therapy for menopause, hysterectomy for abnormal uterine bleeding, ovarian cancer screening, and treatment for incontinence are all situations specific to women’s health in which decisional conflict may arise. O’Connor et al. (1995) developed the decisional conflict scale (DCS), a validated scale that measures (a) perceived uncertainty between options, (b) factors contributing to uncertainty (feeling uninformed, unclear about values, unsupported in decision making), and (c) factors contributing to effective decision making (feeling the choice is informed, values-based, likely to be implemented, and satisfaction with the decision). A total decisional conflict score from 0 (no decisional conflict) to 100 (extremely high decisional conflict) is given, as well as five sub-scores for each factor listed above.

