### **Hypotheses:**

1. A nurse and psychologist-led workshop on pelvic floor disorders will result in decreased decisional conflict compared to standard individual physician-led counselling.
2. Participants will be satisfied with the quality of information shared and will feel comfortable discussing pelvic health in a group setting

**Primary Outcome & Measure:** Change in "Decisional Conflict" between baseline and follow-up, as measured by the Decisional Conflict Scale.

**Secondary Outcome & Measure:** Participant satisfaction with the group workshop. This will be measured using a survey administered immediately following the workshop

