Using a questionnaire, the following demographics will be collected at baseline: age, marital status, education level, household income, ethnicity, predominant type of pelvic floor dysfunction (urinary incontinence, prolapse, both), and previously attempted treatment modalities. Electronic medical records will also be accessed to confirm the principal diagnosis. The Decisional Conflict Scale (DCS) and the Control Preferences Scale (CPS) will also be administered at the baseline visit.

The DCS is a validated scale that measures (a) perceived uncertainty between treatment options, (b) factors contributing to uncertainty (feeling uninformed, unclear about values, unsupported in decision making), and (c) factors contributing to effective decision making (feeling the choice is informed, values-based, likely to be implemented, and satisfaction with the decision). The CPS is a validated tool that assesses the degree to which patients wish to be involved in treatment decision-making. The CPS is a one-item questionnaire with a five-point scale that describes various degrees of involvement in decision-making. Lower scores on the CPS indicate stronger preferences for an active role in decision making while higher score indicate a preference for a passive or collaborative role.

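### The primary outcome is compared by an unadjusted t-test although baseline DCS is collected in both groups; adjusting for baseline (ANCOVA) would give a more precise estimate from the same data.

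*Combined protocol and SAP*

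**What the plan says.** The primary outcome in Section II (Hypotheses) is the change in decisional conflict "between baseline and follow-up, as measured by the Decisional Conflict Scale". The Abstract plans the measurement at both times: "In both groups, decisional conflict will be measured using the validated Decisional Conflict Scale (DCS) at baseline and at the first follow-up clinic appointment". Section III (Study Design and Methodology) confirms the baseline measurement: "The Decisional Conflict Scale (DCS) and the Control Preferences Scale (CPS) will also be administered at the baseline visit".

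The treatment comparison is described twice. The Abstract says "Change in DCS score will be compared using t-tests". Section III (Analysis of results) says "Differences in decisional conflict scores between the intervention and control groups will be compared using unpaired t-tests", without stating whether the scores are changes or follow-up values.

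The only regression in the plan has another purpose: "Linear regression will be done to identify significant predictors of decisional conflict in this population". Neither randomised group nor baseline DCS is named as a term in it. Section IV (Sample size) gives 20 to 40 women per group on grounds of feasibility, with no SD, target effect, significance level or power.

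**The concern.** There are two linked problems. The primary analysis is not uniquely stated, because the Section III wording can be read as a comparison of change or of follow-up scores. And under either reading the test makes poorer use of baseline DCS than a simple regression would.

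A change score fixes the slope on baseline at 1. With equal SDs at the two visits the true slope is rho, which is below 1, so subtracting the whole baseline over-corrects. A group that happens to start higher will tend to show a larger fall through regression to the mean. A follow-up-only comparison makes no correction at all. ANCOVA estimates the slope from the data.

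This matters because the sample is fixed by clinic volume and is small. Hypothesis 1 is comparative, and the results are meant to inform later work. The estimated difference and its confidence interval are the main quantitative product, so avoidable loss of precision is costly.

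**Working it through.** **Inputs from the plan.** Recruitment target 80 and participation of at least 50% (Section IV). 80 × 0.50 = 40 and 80 × 1.00 = 80, so 20 to 40 per group with equal allocation. This reproduces the plan's range. There is no power figure to reproduce.

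**Assumptions, none given in the documents.** Two-sided 5% test; true difference of 0.5 SD of the follow-up score; the same SD (s) at both visits; rho of 0.3, 0.5 or 0.7.

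**Variance per woman entering the group comparison.**
- Follow-up only: s²
- Change score: 2(1 − rho)s²
- ANCOVA: (1 − rho²)s², times 1 + 1/(N − 4) for estimating the slope. The factor is 1.028 at N = 40 and 1.013 at N = 80.

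**ANCOVA against change.** The ratio is (1 − rho²)/[2(1 − rho)] = (1 + rho)/2 = 0.65, 0.75, 0.85. With the slope factor it is 0.67, 0.77, 0.87 at 20 per group and 0.66, 0.76, 0.86 at 40 per group. At rho 0.5, 40 women per group analysed by ANCOVA are worth 40/0.76 ≈ 53 per group analysed by change scores.

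**ANCOVA against follow-up only.** The ratio is (1 − rho²) times the slope factor: 0.94, 0.77, 0.52 at 20 per group and 0.92, 0.76, 0.52 at 40 per group.

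**Change against follow-up only.** 2(1 − rho) exceeds 1 when rho is below 0.5. In that range, subtracting baseline is less precise than ignoring it.

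**Power for 0.5 SD** (noncentral t; N − 2 degrees of freedom for the t-tests, N − 3 for ANCOVA; slope factor included):

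| Per group | rho | Change | Follow-up only | ANCOVA |
|---|---|---|---|---|
| 20 | 0.3 | 26% | 34% | 36% |
| 20 | 0.5 | 34% | 34% | 42% |
| 20 | 0.7 | 51% | 34% | 57% |
| 40 | 0.3 | 46% | 60% | 63% |
| 40 | 0.5 | 60% | 60% | 72% |
| 40 | 0.7 | 81% | 60% | 87% |

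Simulation with 20,000 trials per setting agreed to within about one percentage point. Type I error was 4.7% to 5.1% for the change-score test and for ANCOVA.

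**Chance imbalance.** The standard error of the baseline difference between groups is s√(2/n): 0.32 SD at 20 per group and 0.22 SD at 40. Given a baseline difference D, the change-score estimate is shifted by −(1 − rho)D. At rho 0.5 and 20 per group, an imbalance of one standard error shifts it by 0.5 × 0.32 = 0.16 SD, about a third of the assumed effect.

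**Unequal SDs.** With SD0 at baseline and SD1 at follow-up, the change-score variance minus the ANCOVA variance (before the slope factor) is (SD0 − rho·SD1)², which is never negative. The rho threshold of 0.5 above becomes SD0/(2·SD1).

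**Where ANCOVA loses.** Setting (1 + rho)/2 times the slope factor equal to 1 gives rho of about 0.95 at N = 40 and 0.97 at N = 80. Above that, ANCOVA is less precise than change scores by at most about 3%.

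**The case against.** The strongest reply is that nothing in the plan is invalid. The Abstract's test matches the stated outcome, the change-score comparison is unbiased over repeated randomisation, and its type I error is correct. The trial is a pilot sized by feasibility, so no stated power claim fails. The gains rest on an assumed rho, effect size and equality of SDs, and even with ANCOVA the power at 20 per group is only 36% to 57%. If follow-up scores are meant, the gain at rho 0.3 is only 6% to 8% of the variance. All of this stands, and it makes the point one of efficiency and clarity. It does not remove the point: the plan already commits to a between-group test and to linear regression, and ANCOVA is more precise under both readings across the assumed range.

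A second reply is that ANCOVA cannot repair other features of the design. Section III makes workshop attendance a condition of inclusion. If that removes non-attenders from one group only, baseline differences are no longer purely chance, and the two methods may estimate different quantities. The plan also does not say that baseline DCS is completed before the allocation is revealed, and women in the same workshop may have correlated outcomes. These limits are real but separate. They qualify what any of the three analyses would mean and do not favour the unadjusted t-test.

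**Conclusion.** The concern holds. The plan specifies no baseline-adjusted treatment comparison, and Section III leaves open which score is tested. For rho between 0.3 and 0.7 with equal SDs, ANCOVA reduces the variance of the treatment estimate by about 13% to 34% against change scores. Against follow-up scores alone the reduction is about 6% to 48%. For an assumed 0.5 SD effect, the power gain over change scores is about 6 to 17 percentage points at 40 per group and 6 to 10 at 20 per group. The size depends on a correlation the documents do not give; the direction does not, unless rho exceeds about 0.95. The planned test is valid but inefficient, so this is a change that should be made, not an error that invalidates the trial.

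**What to change.** State one primary analysis, in the same words in the Abstract and in Section III (Analysis of results): linear regression of follow-up total DCS on randomised group and baseline total DCS, reporting the adjusted mean difference in DCS points with its 95% CI. The primary outcome in Section II can stay as change, because with baseline DCS in the model the treatment estimate is identical whether change or follow-up is the dependent variable.

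The questionnaire item on which problem (prolapse or incontinence) concerns the woman most could be a second pre-specified covariate. The unadjusted comparison of change can be kept as descriptive, and the search for predictors should be labelled a separate, exploratory analysis. Add that baseline DCS is completed before the allocation envelope is opened.

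The cost is a few sentences of wording and one degree of freedom for baseline DCS (one more if the second covariate is used). No new data are needed.

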#### **IV. Study Population/Recruitment/Consent process**

##### **Sample size**

For this pilot study, we estimate that recruiting a total of 80 participants will be feasible based on the volume of new consults to the Riverside Hospital Urogynecology Clinic. With a minimum 50 percent participation rate, this would result in a total sample size of 40-80 participants (20-40 per study group).

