### **III. Study Design and Methodology**

This pilot study will be structured as a randomized control trial in which eligible participants will be recruited at the time of their first urogynecology consultation. Participants will be randomized into two groups: (1) standard care (follow up with urogynecologist as usual) or, (2) a workshop on either urinary incontinence (UI) or pelvic organ prolapse (POP), with a follow-up urogynecologist appointment after attendance at the workshop (Figure 1).

Randomization will be done using a computer generated randomization sequence in blocks of 4 or 6. Sequentially numbered envelopes will contain the randomization result, with the group only revealed at time of randomization. Health care providers will be blinded to the treatment group, but participants will be unblinded to treatment group due to the nature of the intervention.

Patients randomized to the intervention group will be asked to select a workshop on either UI or POP based on which pelvic floor disorder they perceive to be most bothersome. Two identical workshops on different dates will be offered for each topic and participants will be required to attend one to be included in the study.

The workshop will be approximately 90 minutes in length. The first 15 minutes will be an information session on either UI or POP led by a Nurse Continence Advisor. The following 60 minutes will comprise a psychologist-led group discussion. The structured discussion will encourage participants to share experiences, thoughts, and feelings on pelvic floor disorders. Resistances and barriers to seeking treatment will be discussed. Decision-making processes will be explored. During the final 15 minutes, participants will be asked to complete a survey to evaluate the workshop. The survey will assess satisfaction with the information provided, quality of group discussion, comfort level with the group experience, and their satisfaction with the roles of the nurse continence advisor and psychologist.

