##### **Exclusion criteria**

- Anal incontinence
- Previous pelvic radiation therapy
- Non-English speaking
- Requirement for a Substitute Decision Maker
- Inability to attend the workshop
- Unwilling to attend an English-language workshop
- Unwilling to complete English-language surveys

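### The 20-40 per group is sound arithmetic, but the rule that only workshop attenders count removes randomised women from one arm and opens the primary comparison to selection bias

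*Combined protocol and SAP*

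**What the plan says.** The Sample size paragraph in section IV is a feasibility estimate based on clinic volume. It holds that "recruiting a total of 80 participants will be feasible" and continues: "With a minimum 50 percent participation rate, this would result in a total sample size of 40-80 participants (20-40 per study group". It does not say whether the 80 are women approached, consented or randomised, or which step the participation rate describes.

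Section III says that "Participants will be randomized into two groups", using permuted blocks of 4 or 6. Women allocated to the workshop then choose a topic. "Two identical workshops on different dates will be offered for each topic", and these women "participants will be required to attend one to be included in the study". No corresponding condition is placed on the usual-care arm.

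The Exclusion criteria list "Inability to attend the workshop". The Abstract says that the DCS is completed in both groups at baseline and at the first follow-up clinic appointment. The primary outcome, under Hypotheses, is the change in DCS between those two times, and Analysis of results compares the groups by unpaired t-test. No analysis population is defined, and no rate is given for non-attendance, withdrawal or missed follow-up.

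**The concern.** The attendance condition takes effect after randomisation and in one arm only. A woman allocated to the workshop who does not come is, on the plain wording, no longer in the study. A control with the same characteristics, who would not have come either, stays in.

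Two things are at stake. First, the stated group size may not be the analysed group size in the workshop arm. Second, and more important, the primary t-test would compare a self-selected part of one arm with the whole of the other. Women who turn up for a group discussion of an embarrassing condition may differ from those who do not in motivation, severity, support or readiness to decide. Each of these could affect how far decisional conflict changes under usual care alone. Randomisation no longer protects a comparison built in this way.

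**Working it through.** **Inputs from the documents.** 80 women; participation of at least 50%, so 0.50 to 1.00 (Sample size); two groups, with equal allocation implied by the per-group figure and compatible with blocks of 4 or 6 (section III); two dates for each of two topics (section III); 5 to 10 women per workshop (Abstract). Attendance and follow-up rates are not given, so any used below are assumptions.

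**1. The plan's own figure.** Total = 80 x participation; per group = total / 2.
- Lower: 80 x 0.50 = 40; 40 / 2 = 20.
- Upper: 80 x 1.00 = 80; 80 / 2 = 40.

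This gives 40-80 in total and 20-40 per group, exactly as stated. It holds if the 50% is consent among 80 women, or completion applied equally to both arms of 80 randomised women. Workshop capacity agrees: 2 x 2 x 5 = 20 to 2 x 2 x 10 = 40 places.

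**2. If the 50% is workshop attendance only.** With 80 randomised as 40 and 40:
- Workshop: 40 x 0.50 = 20 to 40 x 1.00 = 40, as stated.
- Control: 40 throughout.
- Total: 20 + 40 = 60 to 40 + 40 = 80.

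Here the minimum control arm (40) and the minimum total (60) are larger than the plan says, not smaller.

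**3. If the 50% is consent and the attendance rule is then applied.** Randomised: 20-40 per arm. Analysed workshop arm = randomised x attendance; controls are unaffected by the rule. Before any missed follow-up:

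| Assumed attendance | Workshop | Control | Total |
|---|---|---|---|
| 100% | 20-40 | 20-40 | 40-80 |
| 90% | 18-36 | 20-40 | 38-76 |
| 80% | 16-32 | 20-40 | 36-72 |
| 50% | 10-20 | 20-40 | 30-60 |

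Below 100% attendance, the analysed workshop arm is smaller than the number randomised to it. On this reading 20-40 is an upper bound.

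**4. What the rule does to the comparison.** Let a be the attendance proportion and t the effect of the workshop in those who attend. Let d be the difference in mean DCS change under usual care between would-be attenders and would-be non-attenders. With complete follow-up, randomisation puts the same mix of the two in each arm on average.
- Attenders against all controls estimates t + (1 - a) x d.
- All randomised women as assigned estimates a x t, if the workshop has no effect on those who miss it.

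At a = 0.80 the first carries a bias of 0.20 x d and the second is 0.80 x t. At a = 0.50 these are 0.50 x d and 0.50 x t. The documents give neither the size nor the sign of d, so the bias could favour either arm. The as-assigned estimate is diluted, but it is zero when the workshop does nothing; the attenders-only estimate need not be.

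**5. Expected numbers under as-assigned analysis.** If 20-40 are randomised per arm and an assumed 80-90% return for the follow-up DCS: 20 x 0.80 = 16 to 40 x 0.90 = 36 per arm.

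**The case against.** The strongest reply is that the plan's number is correct. It is called a sample size, nowhere an analysed number, and the reading as consent or as two-arm completion reproduces it exactly. That stands.

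A reader might nevertheless infer that no reading yields 20 per arm because only the workshop arm has something to attend. The documents do not support this. Controls also return for a follow-up DCS and can fail to do so, and a 50% completion rate in both arms would already allow for such losses. A reader might also infer that precision is overstated. On the attendance-only reading the opposite is true: sqrt(1/20 + 1/40) = 0.274 against sqrt(1/20 + 1/20) = 0.316, a standard error about 13% smaller than at 20 per group.

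It can also be said that women unable to attend are excluded before randomisation, which should keep non-attendance low. This reduces the loss but does not remove it: a woman able to attend at consent may still not come, withdrawal is allowed, and only two dates are offered for her chosen topic.

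Finally, the attendance sentence may have been meant as an expectation put to participants rather than as an analysis rule. That is possible, but no analysis population is defined elsewhere to override it, and its words make attendance a condition of inclusion. As this is a pilot with no stated power, effect size or standard deviation, no power figure is at risk.

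**Conclusion.** The sample size figure is not an arithmetic error and should not be presented as one. What holds is that section III, followed as written, removes randomised non-attenders from the workshop arm alone, so the primary comparison is between attenders and all controls and is open to selection bias of unknown direction. That conclusion does not depend on how the 50% is read; it requires only that some randomised women miss the workshop and that they differ from attenders in how their decisional conflict would have changed.

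The effect on numbers is conditional. Only if the 50% is consent do the stated 20-40 become an upper bound for the analysed workshop arm. The size of any shortfall depends on an attendance rate that the documents do not give, so the table shows a range and not a forecast. The undefined recruitment and participation terms are a lesser matter of missing detail. The one-sided inclusion rule is the part that merits a change.

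**What to change.** In section III, delete attendance as a condition of inclusion for the primary analysis. In Analysis of results, state that every randomised woman with a follow-up DCS is analysed in the arm to which she was assigned, and collect that DCS at the first follow-up clinic appointment whether or not she attended. Report workshop attendance as a feasibility outcome, and give an attenders-only analysis as supportive.

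In the Sample size section, label 20-40 per group as the number randomised, say which step the 50% applies to, and note that fewer will have a follow-up DCS: for example 16-36 per arm if 80-90% return, marked as an assumed rate.

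The cost is a few sentences and no extra patients; women whom the present rule would discard are kept. The drawback is that the as-assigned estimate includes women who did not receive the workshop and may understate the effect of actually attending, which is why the supportive analysis is worth keeping.
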